Official Title:

The Effect of a Digital Self-Management Education and Support Program on Self-Management, Glycemic Control, and Distress in Young Adults With Type 2 Diabetes Mellitus

NCT Number:

Not yet assigned

Document Title:

Study Protocol

Date of Document:

03 January 2026

Sponsor / Responsible Party:

[name]

Internal Medicine Nurse, Principal Investigator

Affiliation:

Antalya Training and Research Hospital

Akdeniz University, Faculty of Nursing

(Study Chair: [name]. [name])

Note: At the time of document preparation and initial submission to ClinicalTrials.gov, an NCT number has not yet been assigned to this study.

5. Detailed Description

Detailed Description:

Type 2 diabetes mellitus (T2DM) is increasingly being diagnosed in young adults, who often face unique psychological, social, and lifestyle challenges that can negatively affect diabetes self-management, glycemic control, and quality of life. Inadequate self-management behaviors, suboptimal glycemic control, and high levels of diabetes-related distress in this age group increase the risk of acute complications and early onset of chronic complications. Evidence-based diabetes self-management education and support (DSMES) is essential to empower individuals with T2DM to manage their condition effectively. However, traditional face-to-face education programs may be limited by accessibility, time constraints, and lack of continuity, particularly for young adults who are working, studying, or living in different locations.

Digital health interventions, including mobile and web-based platforms, provide an opportunity to deliver flexible, interactive, and personalized DSMES. Nurse-led digital interventions can combine clinical expertise with ongoing support, thereby enhancing engagement, adherence, and behavior change. This study has been designed to evaluate the effect of a comprehensive, nurse-led digital DSMES program on self-management, glycemic control, and diabetes distress in young adults with T2DM.

Study Design

This study is a single-center, parallel-group, randomized controlled trial with an intervention group and an active control group. The trial will be conducted at Van Regional Training and Research Hospital, Endocrinology and Metabolism Diseases Outpatient Clinic (Van, Türkiye). A total of 72 participants diagnosed with T2DM, aged between 18 and 45 years, who meet the eligibility criteria and provide informed consent, will be included. The planned study duration is 24 months, including preparation, recruitment, intervention, follow-up, data analysis, and reporting. The intervention period for each participant is 12 weeks.

Participants

Inclusion criteria include: (1) diagnosis of type 2 diabetes mellitus, (2) age 18–45 years, (3) ability to communicate in Turkish, (4) literacy, (5) access to the internet and ability to use a smartphone, tablet, or computer, (6) no severe physical or mental health condition that would prevent participation, and (7) willingness to provide informed consent and participate in digital follow-up.

Exclusion criteria include: (1) presence of advanced diabetic retinopathy with severe visual impairment that prevents use of digital tools, (2) diagnosis of type 1 diabetes or gestational diabetes, (3) refusal to share necessary information for the study, and (4) participation in another structured DSMES program that could interfere with the intervention.

Withdrawal criteria include: (1) participant request to withdraw at any time, (2) inability to complete follow-up assessments, (3) interruption of internet access or digital communication for more than two weeks, (4) failure to start the program within four weeks after enrollment or participation in less than 50% of the planned intervention, (5) initiation of GLP-1 receptor agonist therapy during the study period, and (6) any new health condition deemed by the investigator to make continued participation inappropriate.

Randomization and Blinding

After baseline assessment, participants will be randomized in a 1:1 ratio to the intervention or active control group using stratified block randomization. Stratification will be based on baseline HbA1c levels (6.5–9% and > 9%) to ensure balanced glycemic status across groups. The randomization list will be generated by an independent researcher. Participants will not be explicitly informed of their group allocation (single-blind design); however, due to the nature of the intervention, the research team delivering the DSMES program cannot be blinded.

Intervention Group: Nurse-Led Digital DSMES Program

Participants in the intervention group will receive a 12-week nurse-led digital DSMES program delivered through a dedicated digital platform. The program is structured according to the ADCES7™ self-care behavior framework (healthy coping, healthy eating, being active, monitoring, taking medication, problem solving, and reducing risks). Key components of the program include:

1. Structured Digital Education Modules: Educational content on T2DM pathophysiology, treatment, self-monitoring, nutrition, physical activity, medication adherence, complication prevention, and psychosocial coping strategies, presented in user-friendly language with visual aids.
2. Interactive Self-Monitoring Tools: Digital forms and tracking cards that allow participants to record glycemic values (fasting and postprandial glucose), HbA1c (when available), blood pressure (if applicable), and self-care behaviors related to the ADCES7™ domains. Participants will receive automated reminders to encourage regular data entry.
3. Nurse-Led Individualized Counseling and Support: Regularly scheduled synchronous and asynchronous communications (such as messaging or calls) with a nurse trained in diabetes education. The nurse will review participants' data, provide tailored feedback, reinforce educational messages, support goal-setting and problem solving, and offer motivational encouragement.
4. Digital Support and Chatbot: A chatbot or FAQ component to provide quick answers to common questions about diabetes management, medication use, hypoglycemia management, and lifestyle behaviors, supplementing nurse support.

5. Multidisciplinary Collaboration (as needed): When necessary, participants may be guided to consult their physician, dietitian, or psychologist for issues identified during the digital follow-up. The nurse will facilitate communication and encourage participants to seek appropriate in-person or telehealth services.

Participants in the intervention group will be encouraged to engage with the platform regularly, follow the educational modules according to the suggested schedule, record their data, and communicate with the nurse as needed.

Active Control Group: Standard Digital Education

Participants in the active control group will be provided with access to the standard Type 2 Diabetes Education Brochure prepared by the Turkish Ministry of Health in PDF format via the digital platform. They will also be able to enter their basic glycemic data into the system. However, they will not receive individualized nurse-led digital counseling, structured DSMES modules based on ADCES7™, or chatbot-based interactive support. This design allows comparison of the comprehensive nurse-led digital DSMES program with standard digitally delivered education materials.

Outcome Measures

Primary and secondary outcomes will be assessed at baseline (pre-intervention) and at the end of the 12-week intervention.

Primary Outcomes:

1. Self-Management: Assessed using the Type 2 Diabetes Self-Management Scale, which evaluates key aspects of diabetes self-care behaviors.
2. Glycemic Control: Assessed by HbA1c levels obtained from laboratory records.

Secondary

Outcomes:

1. Diabetes Distress: Measured using the Diabetes Distress Scale.
2. Additional Glycemic Parameters: Fasting plasma glucose and postprandial plasma glucose values.
3. Self-Management Behaviors: Assessed using the ADCES7™ Self-Management Behaviors Assessment Form and the Type 2 Diabetes Personal Behavior Goal Tracking Card.
4. Metabolic Parameters: Documented with the Type 2 Diabetes Metabolic Parameter Tracking Form and Metabolic Parameter Goal Tracking Card.
5. Usability and Acceptability of the Digital DSMES Program: Assessed using the Mobile Application Usability Scale (MAUS) among participants in the intervention group.

Ethical Considerations

The study protocol has been reviewed and approved by the Akdeniz University Faculty of Medicine Clinical Research Ethics Committee (Approval No: TBAEK-1079) and by the relevant institutional authorities at Van Regional Training and Research Hospital. All participants will be informed about the purpose, procedures, potential risks, and benefits of

the study and will provide informed consent before enrollment. Participation is voluntary, and participants may withdraw from the study at any time without any impact on their routine medical care.

Data confidentiality and privacy will be strictly protected. Personal data and clinical information will be stored securely and used only for research purposes in accordance with applicable ethical and legal regulations. The study involves a behavioral and educational intervention considered to be low risk. Adverse events related to the intervention are not expected; however, any unexpected problems will be documented and managed according to institutional policies.

Expected Contribution

It is anticipated that the nurse-led digital DSMES program will significantly improve diabetes self-management behaviors, enhance glycemic control, and reduce diabetes-related distress in young adults with T2DM compared with standard digital education alone. The results of this study may provide evidence to support the integration of nurse-led digital DSMES into routine care for young adults with T2DM, contribute to the development of innovative education models in diabetes nursing, and inform health policy and clinical practice regarding the use of digital health technologies in chronic disease management.

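### Withdrawal criteria 3 and 4 treat low engagement as withdrawal, so participants who could still be assessed at week 12 may be lost

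*Protocol*

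**What the plan says.** The Participants section of the Protocol has a single list of six withdrawal criteria. The third entry is "3) interruption of internet access or digital communication for more than two weeks". The fourth is "4) failure to start the program within four weeks after enrollment or participation in less than 50% of the planned intervention". They stand beside the participant's own request, "2) inability to complete follow-up assessments", the start of a GLP-1 receptor agonist, and "any new health condition deemed by the investigator to make continued participation inappropriate". The list does not distinguish stopping the programme from leaving follow-up.

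The timing is set elsewhere. Under Study Design, "The intervention period for each participant is 12 weeks". Under Randomization and Blinding, "After baseline assessment, participants will be randomized in a 1:1 ratio to the intervention or active control group". Outcome Measures schedules assessment at baseline and at the end of the 12 weeks, and takes HbA1c, one of the two primary outcomes, from laboratory records. It does not say whether the week-12 assessment still applies after a criterion 3 or 4 event.

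The arms differ in what there is to engage with. For the intervention arm, "Participants will receive automated reminders to encourage regular data entry", and the programme includes "Regularly scheduled synchronous and asynchronous communications (such as messaging or calls) with a nurse trained in diabetes education". The control arm has a PDF brochure and the option of entering glucose data; no scheduled contact is described.

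**The concern.** Criterion 3 and the participation limb of criterion 4 describe behaviour after randomisation. The four-week limb of criterion 4 is counted from enrolment, and the protocol does not state where enrolment falls relative to randomisation.

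If these events end study participation, randomised people are removed according to how they engaged with two very different programmes. Those who remain are then no longer the groups that randomisation made comparable. Reminders and nurse contact could prevent gaps in the intervention arm, or make them easier to notice. Controls, with no scheduled contact, could meet criterion 3 more often if it is read literally. The documents do not show which arm would lose more, so the direction of any bias is open. Precision falls in either case, in a trial of only 72 people.

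**Working it through.** **Reading of the text.**

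1. Criterion 2 already takes out anyone who cannot be assessed. Whatever criteria 3 and 4 add must therefore be people who can be.
2. The neighbouring entries (participant request, inability to complete follow-up, a new illness that rules out continuing) all concern leaving the study. Ethical Considerations also speaks of withdrawing from the study, though only for voluntary withdrawal. Nothing points to a narrower meaning for criteria 3 and 4.
3. Someone offline for two weeks can still give blood and answer a questionnaire at the clinic or by telephone.

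**Timing.** Twelve weeks is 84 days. More than two weeks offline can be reached on day 15 at the earliest, which is 84 − 15 = 69 days before the week-12 assessment. The below-half limb of criterion 4 may be known only near week 12.

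**Bias.** The protocol gives no removal rates or outcome gaps, so the values of p and g below are assumptions. From the protocol: 72 / 2 = 36 per arm. Let p be the share removed in an arm and g the mean of those retained minus the mean of those removed, in SD units, with higher meaning better. Since the full-arm mean is (1 − p) × retained + p × removed, the retained mean exceeds it by p × g. The contrast, intervention (I) minus control (C), therefore shifts by

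shift = p_I × g_I − p_C × g_C.

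| Assumption | Calculation | Shift (SD) |
|---|---|---|
| Net 4 removals, equal gap 0.3 | 4/36 × 0.3 | 0.033 |
| Net 4 removals, equal gap 0.8 | 4/36 × 0.8 | 0.089 |
| Net 7 removals, equal gap 0.3 | 7/36 × 0.3 | 0.058 |
| Net 7 removals, equal gap 0.8 | 7/36 × 0.8 | 0.156 |
| 4 removed per arm, gaps 0.8 and 0.3 | 4/36 × 0.5 | 0.056 |
| 7 removed per arm, gaps 0.8 and 0.3 | 7/36 × 0.5 | 0.097 |
| Equal removal, equal gap | 0 | 0 |

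In the first four rows the shift favours the programme if the intervention arm loses more, and goes against it if the control arm does. In the fifth and sixth rows it favours the arm with the larger gap.

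**Second model for the bias.** A simulation with no true effect removed the least engaged in each arm and assumed a correlation between engagement and improvement. At a correlation of 0.3, removing 20% against 5%, 30% against 10% and 30% against none gave shifts of about 0.07, 0.09 and 0.15 SD towards the arm that lost more. At 0.5 the range was 0.12 to 0.25 SD. At zero correlation there was no bias, and at −0.3 the sign reversed.

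**Precision.** The ratio of confidence-interval widths, from arm sizes alone, is sqrt[(1/n1 + 1/n2) / (2/36)]:

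- 32 and 36: 1.031, about 3% wider
- 29 and 36: 1.059, about 6% wider
- 29 and 29: 1.114, about 11% wider

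**The case against.** The strongest reply is that the harmful reading is inferred. The protocol never says that data collection stops after a criterion 3 or 4 event, and its week-12 schedule carries no exception. That is correct: the text is ambiguous. But site staff must act on it, and the heading and the neighbouring entries point towards ending participation.

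Other points stand in part:

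- Internet access and willingness to be followed up digitally are entry conditions, so some people who meet criterion 3 may be out of reach and already covered by criterion 2. The overlap is only partial, because a gap that later resolves leaves the person assessable.
- HbA1c comes from laboratory records and could be retrieved later if a test was done near week 12 and consent still stands. The permanent loss is then of the questionnaires, and of HbA1c where no test was done.
- For the below-half limb, assessment may be due anyway when the criterion is met. The argument about lost data rests mainly on criterion 3.
- The rates and gaps are assumed, and the 0.03 to 0.16 SD range lies below the standard error of the contrast at full size, sqrt(2/36) = 0.24 SD. This is a risk of unknown size and sign, not a demonstrated bias.
- The analysis set belongs to a statistical analysis plan, which was not available here, and its absence is not criticised. No choice of analysis set can supply outcomes that were never collected.

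**Conclusion.** The concern holds, with medium confidence. As written, criteria 3 and 4 allow assessable participants to be withdrawn for low engagement, and the protocol does not keep them in follow-up. Under the assumed removals and gaps of the first model, the shift is between zero and about 0.16 SD in either direction, and interval widening runs from 3% to 11%. Stronger dependence of outcome on engagement, with more unequal removal, took the shift to 0.25 SD in the second model. None of these rates comes from the protocol. The conclusion rests on the plain reading of the list. If the sponsor intends these criteria to stop only the programme, the same amendment is needed to say so. The point should be settled before participants are lost, because it cannot be repaired afterwards.

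**What to change.** Amend the withdrawal criteria to say that:

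- a criterion 3 or 4 event is recorded as non-adherence or, at most, as discontinuation of the intervention, under the same rule in both arms, and is not withdrawal from the study;
- week-12 outcomes are sought from every randomised participant who has not withdrawn consent, with HbA1c taken from laboratory records or by asking the person to attend for the test, and the scales completed by telephone or at the clinic.

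This gives the statistical analysis plan the data it needs to compare participants as randomised. The cost is a short amendment and a few extra calls or visits. The effect estimate will include people with little exposure to the programme, which is the price of keeping the randomised comparison.

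### A digital interruption of more than two weeks withdraws randomised participants, and the protocol does not say that they are still assessed at week 12

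*Protocol*

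**What the plan says.** The Participants section of the protocol gives one list of six withdrawal criteria. Item 1 is the participant's own request. The next two are "2) inability to complete follow-up assessments" and "3) interruption of internet access or digital communication for more than two weeks". Item 4 includes "participation in less than 50% of the planned intervention", and the last is "6) any new health condition deemed by the investigator to make continued participation inappropriate". The list does not say which items end use of the program and which end participation in the study.

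Randomization and Blinding places allocation straight after the baseline assessment. Outcome Measures sets two time points, baseline and the end of the 12 weeks, and does not say what happens at the second for someone who has been withdrawn.

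The arms differ in how much digital communication they contain. Among other components, the intervention arm has "Regularly scheduled synchronous and asynchronous communications (such as messaging or calls) with a nurse trained in diabetes education". Controls receive the health ministry's brochure "in PDF format via the digital platform" and no individual nurse counseling. Of their data entry the protocol says: "They will also be able to enter their basic glycemic data into the system". Everyone enters under inclusion criterion "7) willingness to provide informed consent and participate in digital follow-up", and internet access is also required of all.

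**The concern.** Modules, tracking tools, nurse contact and chatbot all reach the intervention arm digitally. Going silent for more than two weeks is therefore close to not taking the treatment, and a rule that withdraws people for it selects on engagement after randomisation. Those who go offline may well differ in self-management, distress and HbA1c from those who stay.

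The rule may also bite differently in the two arms. Scheduled nurse contact could reveal a silence sooner, or prevent it. A control who only reads the PDF could be counted as silent or not, because nothing says what communication is expected of that person.

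If withdrawal is taken to mean leaving the study, week-12 outcomes go selectively missing. Analysis sets and missing-data methods may be in an analysis plan that is not shown, and their absence is not the point here. Whether the scales are administered after item 3 is triggered is decided by the protocol, and no analysis can recover a questionnaire that was never given.

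**Working it through.** The protocol states no withdrawal rate, SD, effect size or power, so there is no figure to reproduce. The argument rests first on reading the provisions together; the arithmetic only indicates scale.

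**Reading the provisions together**

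1. Allocation follows baseline and the program lasts 12 weeks, so an interruption during the program comes after randomisation.
2. Item 3 stands beside the participant's request and the inability to complete follow-up, both of which naturally mean leaving the study. Nothing marks item 3 as a milder kind of stop.
3. The only assessment after baseline is at the end of the 12 weeks. No sentence retains withdrawn participants for it, and none excludes them.
4. Item 3 has two halves. Loss of internet access can be applied to both arms. Interrupted digital communication has something to refer to in the intervention arm (scheduled contact), though still no operating definition. In the control arm no contact is scheduled and data entry is optional.

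**Scale, with assumed inputs**

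From the protocol: 72 participants at 1:1, so 36 per arm. Assumed: *m* participants are removed in one arm only; their mean week-12 outcome differs by *d* SD from that of the rest of the arm; the comparison is unadjusted and uses those remaining.

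The mean of the full arm is the mean of those remaining plus *m* × *d* / 36. Dropping the *m* participants therefore shifts the between-arm difference by *m* × *d* / 36 in absolute size.

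| *m* (share of arm) | *d* | Shift in SD |
|---|---|---|
| 1 (2.8%) | 0.25 | 1 × 0.25 / 36 = 0.007 |
| 2 (5.6%) | 0.5 | 2 × 0.5 / 36 = 0.028 |
| 4 (11.1%) | 0.5 | 4 × 0.5 / 36 = 0.056 |
| 4 (11.1%) | 1.0 | 4 × 1.0 / 36 = 0.111 |
| 6 (16.7%) | 1.0 | 6 × 1.0 / 36 = 0.167 |

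- If half of the gap was present at baseline and is adjusted for, the last row becomes 6 × 0.5 / 36 = 0.083 SD.
- If removal is balanced in number and prognosis, the shift is 0.
- For comparison, the standard error of the difference with 36 per arm is √(2/36) = 0.24 SD. The middle case (4 removed, 0.5 SD) is about a quarter of that.
- In a two-sided 5% normal test on those remaining (32 against 36), the middle case raises type I error to about 5.6%. The last row (30 against 36) raises it to about 10%.

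Loss of precision is the smaller matter. For an assumed true effect of 0.67 SD, a two-sided 5% t-test has 80% power with 36 per arm and 75% with 32 per arm.

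**The case against.** The strongest reply is that the point is drawn from silence. The protocol nowhere says that withdrawn participants go unassessed, and the outcome schedule makes no exception for them. That stands, and a reader who infers that these people will not be assessed goes further than the text. What remains is that the text does not protect the assessment. A site following the list as written could reasonably treat item 3 like the participant's own request.

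Other stronger readings are tempting and do not hold:

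- *Item 3 has no meaning for controls.* The internet-access half applies to them, since access and digital follow-up are conditions of entry for all and the brochure comes through the platform. The gap is in the communication half, which is not defined operationally for the intervention arm either.
- *Item 3 contradicts item 4.* Someone offline for 15 of 84 days has 69 days (82%) left and might pass the 50% limit, yet be withdrawn under item 3. But one item concerns a lapse in contact and the other the share of the intervention taken up. One triggering before the other is no contradiction, and the 82% assumes evenly spread participation.
- *Item 6 is a defect.* The investigator's discretion over a new health condition is an ordinary safeguard with no built-in difference between arms. It belongs here only because it shares the silence on week 12.
- *Both primary outcomes are equally at risk.* HbA1c comes from laboratory records and need not depend on being online.

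It is also fair to say that the larger shifts need one-sided removal, a full 1 SD gap and no baseline adjustment.

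**Conclusion.** The point holds as a weakness in a stated rule. Item 3 withdraws randomised participants for an event tied to engagement with the treatment, does not say whether that ends the program or the study, and leaves interrupted communication undefined, especially for controls. Unequal action by arm is possible; the text neither fixes it nor indicates its direction. The self-management scale (primary) and the distress scale (secondary) are the main outcomes at risk.

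The size cannot be derived from the protocol. With 1 to 6 participants removed in one arm only and a gap of 0.25 to 1.0 SD, the shift is 0.007 to 0.17 SD; it is about 0.06 SD in the middle case and zero if removal is balanced. These are illustrations on assumed inputs, and they do not support a claim that the trial will be biased or that the bias favours the program. The change should be made because it is cheap and has to come before data are lost. Confidence is medium.

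**What to change.** - State that item 3 ends use of the program only, and likewise any stop decided by the investigator under item 6.
- Keep every randomised participant who has not withdrawn consent in follow-up. Take week-12 HbA1c from laboratory records and offer the self-management and distress scales by phone, online or at the clinic.
- Apply one definition of interruption in both arms, for example no reply to the same set number of neutral contact attempts after more than two weeks.
- Report reasons for stopping by arm.

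If withdrawn participants are in fact assessed at week 12 and analysed in their randomised arm, these two items no longer cause selection. The cost is protocol wording and a few extra calls or record checks. Some who have stopped the program will still decline the scales, so the loss will be reduced but not abolished.

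### Withdrawal criteria act after randomisation, do not separate stopping the programme from leaving the study, and include a 50% participation rule that cannot apply equally in both arms

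*Protocol*

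**What the plan says.** Under Randomization and Blinding, the order is fixed: "After baseline assessment, participants will be randomized in a 1:1 ratio". The programme therefore starts after allocation.

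Under Participants, one list of six withdrawal criteria follows the eligibility criteria. Beside the participant's own request (1) and failure to complete follow-up assessments (2), it contains:

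- Criterion (3), on connectivity: being offline or out of digital contact for over a fortnight.
- Criterion (4), on taking part in the programme: "failure to start the program within four weeks after enrollment or participation in less than 50% of the planned intervention".
- Criterion (5), on treatment: a GLP-1 receptor agonist being started while the trial runs.
- Criterion (6), which is left to judgement: "any new health condition deemed by the investigator to make continued participation inappropriate".

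The intervention arm has education modules with a suggested schedule, automated reminders and regularly scheduled nurse contact. The active control arm has a Ministry of Health brochure as a PDF; of data entry the protocol says "They will also be able to enter their basic glycemic data into the system". On blinding it says that "the research team delivering the DSMES program cannot be blinded".

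Under Outcome Measures: "Primary and secondary outcomes will be assessed at baseline (pre-intervention) and at the end of the 12-week intervention". The two primary outcomes are the Type 2 Diabetes Self-Management Scale and HbA1c from laboratory records.

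**The concern.** Criteria (3) to (6) describe things that can happen during the trial, after allocation. The protocol does not say whether a participant who meets one of them only stops the programme or also leaves follow-up and analysis. Their place in the same list as the participant's own request points to the second reading. So does criterion (6), which speaks of continued participation, and so does Ethical Considerations, which uses the same verb for leaving the study.

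If that reading is followed, the groups compared at week 12 are no longer the groups randomised. Low engagers would leave mainly the intervention arm, because only there can low engagement be observed against a plan. Where engagement goes with better outcomes, this favours the programme even if it has no effect. Withdrawals for a GLP-1 receptor agonist could push either way, depending on which arm starts the drug more often.

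The loss may also be permanent. With only two assessment times, a self-management questionnaire not given at week 12 cannot be recovered by any analysis plan.

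**Working it through.** **Which criteria can act equally in both arms**

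| Criterion | Intervention arm | Control arm |
|---|---|---|
| (4) under 50% participation | Modules, tracking and scheduled nurse contacts could be counted, though no number is given | Brochure and optional data entry; nothing planned to take 50% of |
| (3) interruption over two weeks | Would come to notice through scheduled nurse contact | No scheduled contact through which to notice it |
| (5) GLP-1 receptor agonist start | Possible; rate may differ by arm | Possible; rate may differ by arm |
| (6) new health condition | Investigator's judgement; blinding of that person not stated | Same |

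**Size, as an illustration**

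From the protocol: 72 participants at 1:1, so 36 per arm. Alpha, power, SD and expected attrition are not given, so the 72 cannot be reproduced and is not disputed here. Assumed: two-sided alpha 0.05, outcome SD 1, no true effect, the lowest-ranked share q of an arm removed on a selection variable (engagement or control), and correlation r of that variable with outcome. A positive difference favours the programme.

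Removing the lowest share q raises the mean of those who remain by r × m(q), where m(q) = φ(z_q)/(1 − q):

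| q | 0% | 5% | 10% | 20% | 30% |
|---|---|---|---|---|---|
| m(q) | 0 | 0.109 | 0.195 | 0.350 | 0.497 |
| remaining of 36 (rounded) | 36 | 34 | 32 | 29 | 25 |

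Bias = r × [m(q₁) − m(q₂)], with q₁ for the intervention arm and q₂ for control. The rejection rate comes from the noncentral t distribution with n₁ + n₂ − 2 degrees of freedom and noncentrality bias/√(1/n₁ + 1/n₂).

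Example, 30% v 10%, r = 0.5: bias = 0.5 × (0.497 − 0.195) = 0.15 SD; noncentrality = 0.151/√(1/25 + 1/32) = 0.565; rejection 8.6%.

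| Withdrawn, intervention v control | r | n₁ v n₂ | False difference (SD) | Rejection | Simulation |
|---|---|---|---|---|---|
| 10% v 10% | any | 32 v 32 | 0 | 5.0% | – |
| 20% v 10% | 0.3 | 29 v 32 | 0.05 | 5.4% | 5.4% |
| 20% v 5% | 0.3 | 29 v 34 | 0.07 | 5.9% | 6.0% |
| 30% v 10% | 0.3 | 25 v 32 | 0.09 | 6.3% | – |
| 30% v 5% | 0.3 | 25 v 34 | 0.12 | 7.2% | – |
| 30% v 10% | 0.5 | 25 v 32 | 0.15 | 8.6% | 9.4% |
| 30% v 5% | 0.5 | 25 v 34 | 0.19 | 11.2% | 12.0% |
| 30% v 0% (extreme) | 0.5 | 25 v 36 | 0.25 | 15.5% | 16.3% |
| 5% v 20% (reverse) | 0.2 to 0.5 | 34 v 29 | −0.05 to −0.12 | 5.4% to 7.6% | 5.5% to 8.1% |

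The simulation column used 40,000 trials per scenario with a two-sample t test. A separate simulation of 20,000 trials per scenario, with removal from the intervention arm only, gave false differences of 0.04 to 0.25 SD and rejection of 5.4% to 16.0% for 10% to 30% removed and r from 0.2 to 0.5. With r = 0, or with equal removal in both arms, it stayed at about 5%.

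**Precision**

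If the 72 contains no allowance for attrition (not stated), the difference detectable with 80% power moves from 0.67 SD (36 v 36) to 0.73 SD (29 v 32) or 0.76 SD (25 v 32).

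**The case against.** The protocol nowhere states that withdrawn participants skip week 12 or are left out of the analysis, and Outcome Measures sets the week-12 assessment without exception. Analysis populations commonly belong to an SAP, which is not at hand. This stands as a limit: the harm is conditional, and the absence of an intention-to-treat statement is not the finding. It does not answer the conduct problem, because an SAP cannot restore questionnaires that were never collected.

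HbA1c comes from laboratory records and could be looked up after withdrawal. This also stands. For HbA1c the exposure depends on whether a week-12 record exists, is retrieved and is analysed; the self-management scale is the more vulnerable outcome.

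No number of modules or contacts is given, so the 50% is undefined in the intervention arm too. True, but a schedule there could be counted; a brochure gives controls nothing to count.

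Every rate and correlation is assumed, strict removal of the lowest-ranked is a harsh selection model, and mild inputs give little: 10% v 5% at r = 0.3 yields 0.03 SD and 5.1%. All of that is fair. The case for correction rests on the rule and the irrecoverable data more than on any one scenario. Likewise, differing rates under criteria (5) and (6) are a possibility that the protocol leaves open, not something it shows.

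**Conclusion.** The concern holds and should be corrected before participants start meeting these criteria. The protocol withdraws people on events after randomisation, does not separate stopping the programme from leaving the study, and includes a participation rule with no counterpart in the control arm. If withdrawn participants are not assessed or not analysed, both primary comparisons are exposed, the self-management scale irrecoverably so.

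Under the assumed inputs, 20% to 30% withdrawn from the intervention arm against 5% to 10% from control gives a false difference of 0.05 to 0.12 SD at r = 0.3, with rejection of 5.4% to 7.2% against a nominal 5%. At r = 0.5, 30% against 5% to 10% gives 0.15 to 0.19 SD and 8.6% to 11.2%. With equal removal on the same measure, or none, there is no bias. The participation rule would tend to favour the programme; the net direction over all criteria cannot be known in advance. Confidence in the size is moderate, because the protocol gives neither rates nor correlations.

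**What to change.** Amend the withdrawal text under Participants and reconcile it with Outcome Measures:

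- State that only withdrawal of consent ends data collection.
- Treat criterion (2) as missing data.
- Record criteria (3) to (6) as dated events after randomisation that do not end follow-up. This concerns data collection only; it alters no clinical care and no treatment rule.
- Offer the week-12 questionnaires to everyone randomised, retrieve week-12 HbA1c from laboratory records, and analyse all in their assigned group.
- Define participation for each arm, or state that the 50% threshold only describes adherence in the intervention arm. Use exclusion below 50% only in a labelled per-protocol sensitivity analysis.
- Record changes in glucose-lowering treatment, with dates, in both arms.

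The cost is protocol wording plus a few record look-ups and reminder calls at week 12. The downside is that the estimated effect may be smaller because low engagers are included, and HbA1c will also reflect treatment changes made after randomisation, which is why these need recording in both arms.
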